### ***2. Heterogeneity in the effect of incentives on early PNC referrals***

I also identify interactions between incentives and baseline TBA characteristics (considered proxies for social preferences) in order to clarify pathways through which the intervention might have worked. I specify a series of equations:

$$y_{ij} = \beta_0 + \beta_1 * T + \beta_2 * T * Var_{ij} + Var_{ij} + X_{ij} + \varepsilon_{ij}$$

Where:

- $Var_{ij}$  is a binary baseline characteristic for TBA  $i$  in village  $j$  previously included in  $X_{ij}$ ;
- $\beta_1$  is interpreted as the treatment effect when  $Var_{ij} = 0$ ;
- $\beta_2$  is the additional effect of  $Var_{ij}$

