## 1. Specific Aims

- a) To determine perceptions of TBA involvement in postnatal care referrals among health care providers, TBAs, and mothers
- b) To define barriers and enablers of TBA involvement in postnatal care referrals
- c) To estimate the impact of performance-based monetary incentives to TBAs on postnatal care referrals of delivery clients
- d) To estimate heterogeneity in impact of performance-based monetary incentives to TBAs on postnatal care referrals of delivery clients

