### Randomized Controlled Trial

The primary outcome for this study is the proportion of delivery clients each TBA successfully refers for postnatal care within 48 hours of delivery.

The team will conduct postnatal care observation surveys in potential study villages. We will select villages that meet the criteria outlined in Section 3.1.

At baseline, trained enumerators will interview TBAs and complete a survey over 60 minutes in a private location chosen by the TBA. The information collected will include demographic data, stated motivation for services, description of services provided, and social network of the TBAs. We will make photo recordings of these interactions (between TBAs and enumerators) for the purpose of presentation as described below.

All TBAs that participate in the study will receive the following:

- Information on the study aims (attached to submission), the need for postnatal care attendance, and verbal encouragement to refer delivery clients to postnatal care within 48 hours of childbirth
- Offer of two-weekly cumulative payouts of \$0.70 per reported delivery they take that is verified by client.
- Each TBA will be assigned an identification number (TBA ID) and randomized with 50-50 probability to the referral incentive or control arm.

TBAs randomized to the referral incentive arm will also receive an offer of two-weekly cumulative payouts of \$2.00 per successful referral of delivery clients to early postnatal care in a facility if it is verified by the client. Delivery clients are women who have given birth assisted by the TBA. Verification is described below.

Thus, the required follow-up surveys will be conducted every two-weeks, consisting of:

- Self-reported deliveries by TBAs obtained via SMS messages sent by TBAs to the study team. TBAs will be asked to send a text message after each delivery they oversee. TBAs will text the name and contact details (phone number and address) of clients delivered over the past two weeks. Two-weekly calls will also be made by the study team to the TBAs to ensure that all deliveries are reported. Data to be recorded includes TBA name as well as TBA delivery client name, phone number, and address.

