### Randomized Controlled Trial Sample Size

Power calculations for this study are based on a comparison of proportion of TBA referrals for early PNC between 2 equal-sized arms for  $H_0=0$  against alternative that it is not. Qualitative evidence of a similar intervention in Nigeria was associated with an average of 5 facility referrals per recruited TBA per month (Akpan & Lah, 2012). The crude birth rate in Ebonyi State is approximately 42 births per 1000 population annually (NPC and ICF International, 2014). If 70 percent of mothers deliver at home, then TBAs can potentially deliver up to 29 births per 1000 population in a year. Thus, a total of 68092 births in Ebonyi State are eligible for referrals in a year, given the state population of 2.4 million (FMOH, 2011). There is an average of 3 TBAs per village and 30 villages per LGA. Thus approximately 90 TBAs work in each of the 13 LGAs in Ebonyi state (1170 TBAs in total). At an average of 60 deliveries per year (68092/1170), there are approximately 5 deliveries per month to each TBA. We have powered the study to detect a difference in proportion of referrals of 0.20, that is 1 extra referral/TBA/month given 5 deliveries. Assuming standard deviation in proportion of referrals equivalent to study by (Rai, 2014) of 0.37 and alpha of 0.05, a minimum sample size of 160 TBAs can detect this effect at the 5 percent level with 90 percent power. With 200 TBAs, we can detect this effect size with over 90 percent power at the 5 percent level. Given an average of 5 TBA delivery clients per month and 5-month intervention period, we expect to enroll at the minimum 4000 TBA clients. With 200 TBAs, we may enroll up to 5000 TBA clients.

The randomized controlled trial study procedures, analysis, and other aspects of the protocol will be registered with the American Economic Association's Registry for randomized controlled trials (<https://www.socialscienceregistry.org/>) prior to baseline data collection.

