## 10. Risks

### 10.1. Are there any reasonably foreseeable risks, discomforts, and inconveniences to participants and/or groups/communities?

No  Yes: If yes; indicate probability, magnitude, and duration of each (note that risks may be physical, psychological, social, legal, and/or economic)

Foreseeable Risks and Mitigation – Focus Group Discussion

Foreseeable Risks and Mitigation – Randomized Controlled Trial

#	Identified risk	Description	Risk mitigation
1.	Loss of time for conduct of antenatal or delivery care may be a discomfort for TBAs.	This is likely to occur for all TBAs for the entire duration of the study.	The activities involved in participation will be clearly identified and the estimated time commitment provided so that potential participants can make an informed decision.
2.	TBAs may fear that research projects will tend to conclude that their services are undesirable as has been the case in the past and may not want to participate in research that furthers such conclusions.	This is unlikely to occur given the study design that focuses on TBA inclusion in formal care via the creation of a new role.	This research project has been designed to create an alternative long-term role for the TBA that has hitherto been excluded from Nigerian health systems; TBAs will be honestly informed about the purpose of research to increase postnatal care use in facilities.
3.	Some of the survey questions may be considered private such as income from services, causing discomfort.	Similar survey questions such as the World Bank Living Standards Measurement Study Survey have not been accompanied by discomfort. Thus we do not expect that this will occur with high probability. There will be a 60 minute baseline survey, and two-weekly 15-minute surveys throughout the study duration.	The information collected using the surveys is justified by the study rationale - to define the TBA for whom the intervention works so that the study findings are easy to translate to policy; The study data management plan will minimize the risk of compromise of information security; All study participants will be informed of their right to withdraw from the study if they find any of the procedures uncomfortable.

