## ***Proposed Empirical Models***

### ***1. Average effect of incentives on early PNC referrals***

I identify the intention-to-treat effect of incentives on the proportion of TBA deliveries referred for postnatal care within 48 hours of delivery (early PNC).

$$y_{ij} = \beta_0 + \beta_1 * T + X_{ij} + \varepsilon_{ij}$$

Where:

- $y_{ij}$  is proportion of delivery clients or neonates (all, with or without delivery complications) referred by TBA  $i$ , in village  $j$  for early PNC;
- $T$  is a dummy variable indicating if the TBA is in the treatment arm;
- $X_{ij}$  is a set of baseline TBA covariates;
- $\beta_1$  is the coefficient of interest and gives the average mean difference in proportion of TBA clients referred between the treatment and the control arm.

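### The heterogeneity model allows only binary moderators and names no standard-error method, so measured moderators would lose information and the interval for the interaction can miss 95% under some conditions

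*SAP*

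**What the plan says.** Protocol section 1 lists as aim (d): "To estimate heterogeneity in impact of performance-based monetary incentives to TBAs on postnatal care referrals of delivery clients". The only analysis for that aim is the interaction model in SAP section 2, which also appears as the second equation in Protocol 5.1. Both define the moderator in the same way: Var "is a binary baseline characteristic for TBA" i in village j. It is drawn from the baseline covariates X, which are not limited to binary variables in either document. No moderator is named and no cut-point is given.

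The outcome, defined in SAP section 1, is the "proportion of delivery clients or neonates (all, with or without delivery complications) referred by TBA", so there is one value between 0 and 1 per TBA. Both equations end in a single error term. Neither document states a distribution or variance for that term, or whether standard errors are classical, robust or clustered.

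The moderators would come from the baseline interview, which covers "demographic data, stated motivation for services, description of services provided, and social network of the TBAs" (Protocol 4.6). The risk table in Protocol 10.1 adds: "Some of the survey questions may be considered private such as income from services". It justifies such questions by the wish to describe the TBAs for whom the intervention works, which is aim (d).

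**The concern.** There are two separate issues.

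- **Scale.** A covariate such as age, income or network size can enter the main model as recorded, but must be turned into two groups before it can serve as a moderator. Cutting a measured variable throws away information, and the choice of cut-point is left open.
- **Standard error.** The variance of a proportion depends on its mean. If TBAs with Var = 1 have a different referral level from the rest, their proportions may also have a different spread. A pooled variance is then dominated by the larger group, while the standard error of beta2 is driven mainly by the smaller one. The interval can come out too narrow or too wide.

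What is at stake is the precision and honesty of the results for aim (d), already the least precise part of the trial. The main comparison is not exposed in the same way, because its two arms are about equal in size.

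**Working it through.** **Inputs from the documents.** 160 to 200 TBAs, allocated 1:1; 5 deliveries a month for 5 months = 25 per TBA. The study is powered to "detect a difference in proportion of referrals of 0.20", with a standard deviation "of 0.37 and alpha of 0.05", two-sided, at 90% power.

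**Inputs assumed.** The documents give no baseline referral rate, no share of TBAs with Var = 1 and no moderator distribution. All of these are assumed below and varied.

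**1. The plan's own sample size (main effect only).** n per arm = 2 × (1.960 + 1.282)² × 0.37² / 0.20² = 71.9, so 72 per arm or 144 TBAs. The plan states 160, at which power is 92.8%. The difference is on the safe side and does not bear on this point. No sample size is given for beta2.

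**2. Precision of beta2 at best (50/50 split).** SE = 0.37 × √(4/(N/4)). At N = 160 this is 0.37 × √(4/40) = 0.117; at N = 200 it is 0.37 × √(4/50) = 0.105. Power for an interaction as large as 0.20 is 40% and 48%.

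**3. Information lost by splitting a measured moderator with a linear interaction.** The share kept by a split at quantile q is φ(z_q)² / (q(1−q)) for a normal moderator and 3q(1−q) for a uniform one.

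| Split | Normal: lost | Uniform: lost |
|---|---|---|
| 50/50 | 1 − 0.399²/0.25 = 36% | 1 − 0.75 = 25% |
| 75/25 | 46% | 44% |

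For the normal median split, 160 TBAs act like 160 × 0.637 = 102, and 200 like 127. Power of 80% falls to Φ((1.960 + 0.842) × √0.637 − 1.960) = 61%. A trait recorded as binary loses 0%.

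**4. Pooled-variance standard error of beta2.** Take the four arm-by-Var cells, an incentive effect of 0.20 in both groups, and the same within-TBA correlation ρ in every cell. The variance of a TBA's proportion is then p(1−p) × [ρ + (1−ρ)/25]. The bracket cancels from the ratio of the pooled to the true standard error.

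Example: 20% in Var = 1, so cells of 64, 64, 16 and 16; control rates 0.40 (Var = 1) and 0.05 (Var = 0).

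- Var = 0: 0.05×0.95 + 0.25×0.75 = 0.235. Var = 1: 0.40×0.60 + 0.60×0.40 = 0.480.
- Pooled: (63×0.235 + 15×0.480)/156 = 0.141. Estimated variance: 0.141 × (2/64 + 2/16) = 0.0220.
- True variance: 0.235/64 + 0.480/16 = 0.0337.
- SE ratio = √(0.0220/0.0337) = 0.81. Coverage = 2Φ(1.96 × 0.81) − 1 = 89%.

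The same formula in other settings, as SE ratio and coverage:

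| Control rate, Var = 1 v Var = 0 | 15% in Var = 1 | 20% | 30% |
|---|---|---|---|
| 0.40 v 0.05 | 0.78, 87.4% | 0.81, 88.7% | 0.87, 91.2% |
| 0.40 v 0.10 | 0.85, 90.3% | 0.87, 91.1% | 0.91, 92.6% |
| 0.30 v 0.15 | 0.91, 92.6% | 0.92, 93.0% | 0.95, 93.7% |
| 0.40 v 0.20 | 0.94, 93.4% | 0.95, 93.6% | 0.96, 94.1% |
| 0.40 v 0.30 | 0.99, 94.6% | 0.99, 94.7% | 0.99, 94.8% |
| 0.10 v 0.40 | 1.18, 97.9% | 1.15, 97.6% | 1.10, 96.9% |

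At a 50/50 split the ratio is 1 and coverage 95% in every row. Beta-binomial simulations of 160 TBAs agree: 87-92% for the first two rows, about 93-95% for the middle three and 97-98% for the last. HC3 covers about 95% throughout.

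**5. What unequal groups do alone.** With 80/20 or 90/10 groups whose variance differs by arm but not by Var, simulated pooled coverage stays at 94.9-95.5%.

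**6. More extreme settings.** With rates of 0.30/0.50 in the smaller group and 0.05/0.10 in the larger, pooled coverage falls to 83% at 80/20 and 77-78% at 90/10. At 90/10 (8 TBAs per arm in the small group) HC3 ranges over about 93-96% across the settings tried.

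**The case against.** The case on the other side is substantial, and much of it stands.

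- **Dichotomising is not stated.** A reader might infer that every moderator is forced into two groups and that a third of the information is thrown away. The documents do not support that. They name no moderator and no cut-point, and they describe the moderators only as proxies for social preferences. The interview list gives topics rather than variable types. Income appears in a risk table and is nowhere made a moderator. The loss is conditional on a measured item being used.
- **Equal variance is not stated.** Writing one error term does not impose a common variance. The plan is silent, so this is an omission and not a wrong assumption.
- **Unequal groups alone do no harm.** A reader might infer that imbalance by itself spoils the interval. Step 5 shows that it does not. For moderate gaps in referral rate the error is small.
- **Heterogeneity is explanatory.** The SAP uses it to clarify pathways, and no conclusion on whether the incentive works depends on it.

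What remains is that the moderator's definition, as written, leaves no room for a measured variable in the only analysis of a stated aim, and that the standard-error method is missing where it can matter.

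**Conclusion.** The point holds in a conditional form. If a moderator was recorded as a count, amount or age, the model as written requires a cut. A median split then costs 25% to 36% of the information on the interaction, assuming a linear interaction and a uniform or normal moderator. If default pooled-variance standard errors are used, and the groups differ both in size and in outcome variance, the interval for beta2 departs from 95% in a direction that cannot be known in advance. The departure is slight for control-rate gaps of 10-20 points when the smaller group has the higher rate, and reaches 87-92% or 97-98% for the larger gaps shown. These coverage figures rest on assumed rates, 25 deliveries for every TBA and no correlation within villages.

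The main effect of the incentive is not called into question. The change is still worth making, because aim (d) has little precision to spare: even at a 50/50 split, power for an interaction of 0.20 is under one half.

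**What to change.** In SAP section 2 and the matching equation in Protocol 5.1:

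1. Where the text says that Var "is a binary baseline characteristic for TBA", define it instead as a baseline characteristic kept on its recorded scale, with continuous and count items centred and binary or nominal items entered as indicators.
2. For continuous items, report the estimated incentive effect at the 25th and 75th percentiles of the moderator.
3. State that Model 2 uses HC3 (heteroskedasticity-consistent) standard errors.

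The cost is a few lines of text, with no new data or participants. The downsides are small: a linear interaction is assumed for measured items, and the presentation is slightly less simple. A binary split fixed in advance may be kept as a secondary display. HC3 does not deal with correlation between TBAs in the same village; that is a separate point and needs its own provision.
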